## APPENDIX:

### NIAID 8-POINT ORDINAL SCALE FOR CLINICAL IMPROVEMENT

- The ordinal scale is an assessment of the clinical status at the first assessment of a given study day. The scale is as follows: 8) Death; 7) Hospitalized, on invasive mechanical ventilation or extracorporeal membrane oxygenation (ECMO); 6) Hospitalized, on non-invasive ventilation or high flow oxygen devices; 5) Hospitalized, requiring supplemental oxygen; 4) Hospitalized, not requiring supplemental oxygen - requiring ongoing medical care (COVID-19 related or otherwise); 3) Hospitalized, not requiring supplemental oxygen - no longer requires ongoing medical care; 2) Not hospitalized, limitation on activities and/or requiring home oxygen; 1) Not hospitalized, no limitations on activities.

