- Proportion of patients alive and free of invasive mechanical ventilation at 90 days.
- Proportion of patients alive and free of invasive mechanical ventilation at 120 days.
- Proportion of patients alive and free of invasive mechanical ventilation at 150 days.
- Proportion of patients alive and free of invasive mechanical ventilation at 180 days.
- Proportion of patients alive and free of invasive mechanical ventilation at 270 days.
- Proportion of patients alive and free of invasive mechanical ventilation at 360 days.
- National Institute of Allergy and Infectious Diseases (NIAID) 8-point ordinal scale (see Appendix): Day 0, 2, 5, 7, 14, 28, 60, 180 and 360.
- Need for vasopressors
- Need for renal replacement therapy
- Need for extracorporeal membrane oxygenation (ECMO)

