3.4 Software: All analyses will be performed utilizing SAS® version 9.4. All statistical tests will be conducted at the 5% Type I error rate (two-sided). When multiple tests are conducted, the chance of finding a significant difference in one of the tests, when in fact no difference exists, is greater than the stated Type I error rate. The investigators are aware of the multiple testing issues and will interpret results with caution and use confidence intervals where possible.

4.0 Analysis of demographic and baseline data:

The demographic variables for this study include age, gender, race, ethnicity, and BMI, etc. The baseline clinical characteristics include disease severity, symptoms, comorbid conditions, days

from COVID-19 symptom onset, and baseline blood lab results, etc.

Descriptive statistics for baseline and demographic variables will be presented for patients randomized to each of the treatment arms and overall. Descriptive statistics will include N, mean, standard deviation, median, 25th and 75th percentiles, minimum and maximum for continuous variables and proportions and percentages for categorical variables. In general, randomization is expected to produce balance at baseline between the two arms of the trial, formal statistical comparisons of treatment groups with respect to baseline characteristics will not be necessary. However, since this is a relatively small study, the differences in baseline characteristics between the treatment arms will be evaluated exploratorily for better understanding the study population. The updated CONSORT statement no longer recommends formal testing of statistical significance of differences between baseline characteristics.

5.0 Efficacy analyses:

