- The response of being alive and free invasive mechanical ventilation at 60 days is a binary response and will be analyzed using the same methods as that for the primary efficacy outcome.
- National Institute of Allergy and Infectious Diseases (NIAID) 8-point ordinal scale on Day 0, 2, 5, 7, 14, 28, 60, 180 and 360 will be considered as longitudinal data. The distributions of the data will be examined visually first and further collapsing will be considered. Collapsed data will be analyzed in the generalized linear mixed effect model or multinomial logistic regression with the generalized estimating equation approach.
- Proportion of patients alive and free of invasive mechanical ventilation at 60, 90, 120, 150, 180, 270 and 360 days will be estimated from the Kaplan-Meier survival for the time to mechanical ventilation-free survival over the first year. The difference in these proportions between the two treatment groups will be evaluated by the log-rank test and further in Cox regression adjusting for the baseline covariates. For the analysis of mortality over the first year, additional adjustment for dynamic mechanical ventilation effect will be considered by including being on ventilation as a time-vary covariate in the Cox regression.
- Need for vasopressors is a binary response and will be analyzed using the same methods as for the primary efficacy outcome.
- Need for renal replacement therapy is a binary response and will be analyzed using the same methods as for the primary efficacy outcome.
- Need for extracorporeal membrane oxygenation (ECMO) is a binary response and will be analyzed using the same methods as for the primary efficacy outcome.

6.0 Other safety analyses:

Analysis of adverse event (AE) data will primarily be descriptive based on CTCAE coding of events. The proportion of subjects experiencing a severe AE and the proportion experiencing a Grade 3 or higher will be recorded. AE will be compared to published data.

7.0 Sample size estimation and power analysis:

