This trial is intended to be an early stage and proof of concept study with the primary goal to collect reliable data and obtain sufficient evidence for future trials. Thus, the emphasis of the study is an exploratory estimation of effect size and incidence of adverse events in terms of eosinophilia; it is not considered as a pivotal trial for efficacy at this time. Therefore, a larger significance level (one-sided alpha=0.1), and the sample size is pre-selected based on the feasibility. Given the current decline trend in the incidence of COVID-19 positive cases, we anticipate to enroll 40 patients realistically into this randomized clinical trial, which shall be sufficient for us to collect reliable and interpretable data for proof of concept to inform future trials. The COVID-19 hospitalization data from our University of Virginia Health System between March 2020 and April 6, 2021 showed that 79.5% of COVID-19 inpatients were alive and free of mechanical ventilation at 28 days under the usual care. With 40 patients that are deemed to be feasible, we would expect Dupilumab to improve a margin of 17.7% in the proportion of patients alive and free of mechanical ventilation at 28 days. That is, it is anticipated that 97.2% of patients being alive and free of ventilation at 28 days in the Dupilumab arm. The power analysis is conducted using the one-sided Score test (Farrington & Manning) with 75% power and 10% type I error.

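### For the NIAID 8-point scale, SAP 5.3.2 leaves grouping, link and blinding of inspection open, so the scale's order could be dropped or a cut-point chosen by arm

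*SAP*

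**What the plan says.** SAP Section 2.2.2 lists the scale as a secondary outcome at nine visits: "8-point ordinal scale (see Appendix): Day 0, 2, 5, 7, 14, 28, 60, 180 and 360". The Protocol appendix defines it as an ordered status. Level 1 is at home without limitation, and the other end is given by "The scale is as follows: 8) Death".

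The analysis is one bullet in SAP Section 5.3.2. It treats the data as longitudinal and continues: "The distributions of the data will be examined visually first and further collapsing will be considered". The next sentence is "Collapsed data will be analyzed in the generalized linear mixed effect model or multinomial logistic regression with the generalized estimating equation approach". The documents do not state:

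- the number of categories, the cut-points or a rule for merging;
- the link (cumulative or generalized logit), or how to choose between the two models;
- an analysis for the scale if it is left ungrouped;
- whether the inspection is pooled over arms or blinded;
- adjustment for the oxygen stratum (15 L or less, or more than 15 L) used to randomise in SAP Sections 1.2 and 1.4. The example covariates in Section 5.1 are age, sex, race and co-morbidities;
- how a patient who has died is scored at later visits.

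Other parts of the SAP are tighter. Eosinophilia has a fixed threshold (Section 2.2.1), and the interim biomarker look is done by a third party with the investigators blinded (Section 3.3).

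**The concern.** The information in an ordinal scale lies in its order. A generalized-logit model ignores that order, and a binary model keeps only one split of it. Both fit the wording of Section 5.3.2, and at 20 patients per arm either can cost a good deal of power.

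The second issue is when the grouping is decided. If the distributions are viewed by arm, the cut can follow the observed difference. The nominal error rate then no longer holds, and the estimate at the chosen cut is pushed away from no effect. That matters even in an exploratory trial, because SAP Section 7.0 puts the emphasis on estimating effect size for future trials.

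**Working it through.** **The plan's own figure.** The SAP gives no power for this scale. Its one power statement (Section 7.0) concerns the binary primary outcome: 79.5% against 97.2%, 20 per arm, one-sided 0.10. Exact enumeration of the score test gives 75.1% power with actual size 9.9%, so the stated 75% reproduces. It does not bear on the ordinal scale.

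**Inputs from the SAP.** 40 patients randomised 1:1 (Section 1.2), so n = 20 per arm and N = 40. Tests are two-sided at 5% (Section 3.4).

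**Assumptions.** The documents give no distribution over the eight levels. Three control distributions were assumed (percent in levels 1 to 8). Each puts 20.5% in levels 7-8, the complement of the SAP's 79.5%:

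- A, mostly at home: 35, 25, 2, 3, 7, 7.5, 8.5, 12
- B, spread: 15, 20, 5, 10, 15, 14.5, 10.5, 10
- C, two clusters: 50, 25, 0.5, 1, 1.5, 1.5, 5.5, 15

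A single visit is analysed. The treatment effect is a common odds ratio OR. With c the control probability of being at or below a level, the dupilumab probability is c' = OR·c / (1 − c + OR·c). For example, at the split between levels 6 and 7 with OR = 3, c' = 3 × 0.795 / (0.205 + 2.385) = 0.921, so levels 7-8 fall from 20.5% to 7.9%.

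**Tests.**

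- Ordered: Wilcoxon with ties, which is the score test of proportional odds. Z = [W − n(N+1)/2] / √V, with V = (n²/12)·[(N+1) − Σ(t³ − t)/(N(N−1))], where W is the rank sum of one arm and t is the number of patients at each level.
- Nominal: Pearson chi-square on the 2 × 3 table (levels 1-2, 3-6, 7-8).
- Binary: pooled two-proportion z-test at each of the seven cuts.

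Each setting used 40,000 simulated trials. The standard error at 40% power is √(0.4 × 0.6 / 40,000) = 0.25 points.

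**Hand check of one cell.** Cut between levels 6 and 7, OR = 3:

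- the difference is 0.921 − 0.795 = 0.126 and the pooled proportion is 0.858;
- the null standard error is √(2 × 0.858 × 0.142 / 20) = 0.110;
- the alternative standard error is √[(0.795 × 0.205 + 0.921 × 0.079) / 20] = 0.109;
- power ≈ Φ[(0.126 − 1.96 × 0.110) / 0.109] ≈ Φ(−0.83) ≈ 20%. The simulation gives 19.8-20.1%.

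**Power (%) at OR = 3**

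| Analysis | A | B | C |
|---|---|---|---|
| Ordered, 8 levels | 44.6 | 48.0 | 39.2 |
| Ordered, 3 levels | 34.1 | 42.6 | 24.0 |
| Nominal, 3 levels | 24.1 | 32.9 | 15.3 |
| One binary cut, worst to best | 9.7-37.3 | 7.0-37.6 | 14.2-37.8 |

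A separate run compared the full scale with five ordered levels (1, 2, 3-5, 6-7, 8). The powers were 44.0 against 43.8, 47.9 against 47.1, and 38.7 against 38.7, a loss of 0.2, 0.8 and 0.0 points.

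From eight ordered levels to three nominal ones the loss is 20.5, 15.1 and 23.9 points. Coarse merging accounts for 10.5, 5.4 and 15.2 of these, and dropping the order for a further 10.0, 9.7 and 8.7.

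At OR = 4 the pattern is the same: ordered 54-67%, three-level nominal 21-48%, one binary cut 8-54%.

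**False-positive rate at nominal 5% (OR = 1)**

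| Choice of analysis | Range over A, B, C |
|---|---|
| Ordered, 8 levels | 4.7-5.1% |
| Cut nearest the median of the pooled data | 4.0-4.4% |
| Best of three cuts, chosen by arm | 7-12% |
| Best of seven cuts, chosen by arm | 13-21% |

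**The case against.** The text commits to little. A reader might infer that the scale will certainly be grouped, but the SAP says only that grouping will be considered; the looseness is that no analysis is given for the alternative. A reader might also infer that multinomial regression must ignore order. That is true of the generalized logit, but a multinomial response can equally be fitted with a cumulative logit, by estimating equations or in a mixed model. Both objections stand, so the power loss is something the plan allows, not something it has chosen.

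Looking for sparse cells is ordinary practice with 40 patients. At Day 0 everyone is in hospital and invasive ventilation is excluded, so levels 1, 2 and 8 are empty and level 7 nearly so. Grouping as such is harmless if it merges neighbours and keeps the order, as the five-level result shows.

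A reader might take 13-21% to be the plan's error rate. The documents do not support that: they speak of distributions without saying whose, and a cut chosen on pooled data causes no inflation. The figure shows what is at risk if the inspection is by arm.

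The SAP also disclaims formal hypothesis testing (Section 5.1) and promises cautious reading with confidence intervals (Section 3.4). This lowers the stakes without closing the gap, since an interval at a cut selected by arm carries the same selection bias.

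**Conclusion.** The point holds as an under-specification. Section 5.3.2 permits an analysis that drops the order or uses a cut chosen from the arm comparison, and it requires neither. If order is dropped on three levels, the cost is about 15 to 24 points of power at an odds ratio of 3. A single binary cut costs anything from about 1 point (best cut, distribution C) to about 41 points (worst cut, distribution B).

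These figures compare methods and do not forecast the planned analysis. They rest on assumed level distributions, a single visit rather than nine, and an effect that follows proportional odds, which favours the ordered test. The nominal figures are for three levels because the plan models grouped data; an eight-level nominal analysis would describe something the SAP does not propose.

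Severity is low. This is one of many secondary outcomes of an exploratory parent trial, and the follow-up Protocol carries the scale only in its appendix, not among its endpoints.

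**What to change.** Rewrite the bullet in SAP Section 5.3.2 as follows:

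- Keep the longitudinal analysis, and name a cumulative-logit (proportional-odds) model on the full ordered scale as the main analysis.
- Adjust for the oxygen stratum used in the randomisation.
- Score death as 8 at every later visit. Protocol Section 6.2 reports 7 deaths among 40 patients by Day 60, and SAP Section 8.0 otherwise assumes missing at random, so Days 180 and 360 depend on this.
- If sparse levels must be merged, merge only adjacent levels, by a rule fixed in advance or set on pooled, blinded data.
- Label any other grouping post hoc. This includes a grouping chosen for visits whose results by arm have already been seen; the Protocol reports 60-day findings of the parent trial by arm.

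The cost is SAP wording, with no new data. The small downside is that the summary relies on a common odds ratio for its interpretation, so the level frequencies by arm should be shown beside it.

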5.2 Primary efficacy outcome

The primary efficacy endpoint of this study is a binary indicator for whether a patient would be alive and free of invasive mechanical ventilation at 28 days. The outcome will be summarized as the proportion of patients alive and free of invasive mechanical ventilation at 28 days and the difference in the proportions between the two study arms will be evaluated with Chi-square test. The odds ratio of being alive and free of invasive mechanical ventilation at 28 days for Dupilumab vs. placebo and its 95% confidence interval (CI) will be estimated in logistic regression, adjusting for potential baseline characteristics if necessary.

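### SAP 5.3.2 assigns the difference between arms in seven landmark ventilation-free proportions to one log-rank test and a Cox model, neither of which compares the arms at any landmark; Day 60 also has a second analysis, and neither is named as main

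*SAP*

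**What the plan says.** SAP 2.2.2 lists the ventilation-free outcome as a separate proportion at each day, ending with "Proportion of patients alive and free of invasive mechanical ventilation at 360 days". Day 60 appears there once.

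SAP 5.3.2 says that the proportions at the seven days "will be estimated from the Kaplan-Meier survival for the time to mechanical ventilation-free survival over the first year". The next sentence reads "The difference in these proportions between the two treatment groups will be evaluated by the log-rank test", followed by Cox regression with adjustment for baseline covariates. That bullet gives no fixed-time comparison and no confidence interval for a difference at any landmark. It does not say what counts as the event.

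Two bullets earlier the same section states: "The response of being alive and free invasive mechanical ventilation at 60 days is a binary response", to be analysed by the methods used for the primary outcome. Under SAP 5.2 those are a Chi-square test and a logistic odds ratio with 95% CI, applied to a "binary indicator for whether a patient would be alive and free of invasive mechanical ventilation at 28 days".

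**The concern.** The outcome is a set of seven proportions, but the comparison attached to them is a test of the whole curve. A reader of the results would see seven pairs of percentages beside one p-value and would naturally take it as evidence about each pair. It is not, and the hazard ratio does not supply the missing differences.

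Two further ambiguities follow. Day 60 will have two results, from different methods, with no stated priority. And because the event is undefined, the label (alive and off the ventilator at Day X) and the curve may describe different things. A Kaplan-Meier curve cannot return a patient to the event-free state after extubation.

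What is at stake is estimation. SAP 7.0 makes exploratory estimation of effect size the emphasis of the trial, and SAP 3.4 promises confidence intervals where possible. This bullet provides neither for the outcomes it names.

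**Working it through.** **The plan's own figure.** The SAP gives no figure for the landmark outcomes. The nearest is the 75% power for Day 28 in SAP 7.0 (79.5% v 97.2%, one-sided 10%, score test). Exact enumeration with 20 per arm gives 0.751, so it reproduces. The point does not depend on it, but the two rates are reused in step 3.

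**Inputs from the documents.** 40 patients, 1:1, so 20 per arm (SAP 1.2); two-sided 5% tests (SAP 3.4); patients on invasive ventilation at enrolment excluded, so everyone starts event-free (SAP 1.5); 7 of 40 dead by Day 60 (Protocol 6.2).

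**Step 1. Constructed data (an assumption, not trial data).** Six first events per arm and no censoring. Placebo events fall on Days 2, 4, 6, 9, 12 and 20; dupilumab events on Days 70, 100, 130, 170, 250 and 340.

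Log-rank: at each event, add the share of patients at risk who are in the dupilumab arm. Expected dupilumab events = 20/40 + 20/39 + 20/38 + 20/37 + 20/36 + 20/35 + 20/34 + 19/33 + 18/32 + 17/31 + 16/30 + 15/29 = 6.53. Observed = 6. Variance = 2.97. Chi-square = (6 − 6.53)² / 2.97 = 0.095 (unrounded inputs), p = 0.76.

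Landmark comparison: z = (p_D − p_P) / √(2·p̄(1 − p̄)/20), which is the Chi-square test without continuity correction. At Day 60, p̄ = 0.85 and z = 0.30 / 0.113 = 2.66.

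| Day | Placebo | Dupilumab | Difference (points) | p |
|---|---|---|---|---|
| 60 | 70% | 100% | 30 | 0.008 |
| 90 | 70% | 95% | 25 | 0.037 |
| 120 | 70% | 90% | 20 | 0.11 |
| 150 | 70% | 85% | 15 | 0.26 |
| 180 | 70% | 80% | 10 | 0.47 |
| 270 | 70% | 75% | 5 | 0.72 |
| 360 | 70% | 70% | 0 | 1.00 |

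One p-value of 0.76 stands for differences that run from 30 points to none.

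**Step 2. Same timing pattern, simulated.** With a 30% event risk per arm, placebo events in Days 0–28, dupilumab events in Days 61–360 and 4,000 trials, log-rank rejects in 7.7% and the Day 60 comparison in about 90%.

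**Step 3. Timing confined to the acute phase (assumed).** With all first events in Days 0–60 and the SAP's 79.5% v 97.2%, log-rank and the Day 60 comparison each reject in about 41% of trials and agree in over 99.9%. With 60% v 90% they agree in about 98%.

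**Step 4. First event versus status on the day.** If F is the share with a first event (ventilation or death) by Day 60, the curve without censoring gives 1 − F. The share alive and off the ventilator on that day is 1 − F plus the share extubated and alive. Seven deaths cap the pooled proportion alive at Day 60 or later at 33/40 = 82.5%. If F were 12/40 = 30% (assumed), the curve gives 70%. At most 12 − 7 = 5 of those patients could be extubated survivors, so the status proportion lies between 70% and 82.5%. If F were 7/40 = 17.5%, the gap is zero. The documents give no count of patients ventilated or extubated, so the actual gap cannot be computed.

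**Step 5. The two Day 60 analyses.** They give the same proportion if the outcome means never ventilated through Day 60 and nobody is censored before then. They can differ on extubated survivors (step 4) and on withdrawals. Kaplan-Meier would normally censor withdrawals, whereas SAP 8.0 counts unknown status as an event, but only for Day 28. Whether that rule extends to Day 60 is not stated.

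**The case against.** The strongest reply is that the mismatch rarely matters in practice. Invasive ventilation and death in acute COVID-19 would be expected to cluster early, and step 3 shows that the two approaches then almost always reach the same decision. The timing in steps 1 and 2 was chosen to separate them. This stands as a limit on the numerical consequence. It does not supply the missing landmark differences and intervals, because even when the tests agree, a log-rank p-value and a hazard ratio are not a risk difference at Day 180.

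A reader might infer that the Kaplan-Meier proportions must understate patients alive and off the ventilator, perhaps by 10 to 15 points (assuming 20 to 30% ever ventilated and half extubated alive). The documents do not support that. The SAP never defines the event, and the outcome can be read as never ventilated through Day X, in which case nothing is understated. The implied status proportions of 85 to 90% also exceed the 82.5% ceiling set by the deaths in Protocol 6.2. Recovered patients are in any case not lost from the report: the NIAID ordinal scale records status at Days 60, 180 and 360.

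A reader might also infer that every landmark should simply become a binary status outcome like Day 28. That would give up the handling of censoring at Days 90 to 360. SAP 1.2 describes follow-up of up to 60 days, SAP 8.0 expects dropout and missed visits, and its rule for unknown status covers only Day 28.

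Finally, these are secondary outcomes in a trial that disclaims formal hypothesis testing (SAP 5.1). That also stands, and it limits the consequence to interpretation.

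**Conclusion.** The point holds in a limited form. SAP 5.3.2 names a comparison that does not address the seven proportions it is attached to, and this is so however freedom from ventilation is read. The divergence can be large when hazards are strongly non-proportional (p = 0.76 against 0.008 in constructed data) and is negligible to small when first events are confined to the acute phase (98% agreement or more). Which pattern applies cannot be told from the documents.

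Day 60 has two analyses with no stated priority. Whether the curve also misstates the labelled outcome depends on a definition that the SAP does not give; the size of any such gap is unknown.

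No primary conclusion and no confirmatory error rate depends on this. The effect is on how the one-year ventilation-free results are read and on whether they yield usable effect estimates for future trials.

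**What to change.** Amend SAP 5.3.2, with matching labels in SAP 2.2.2:

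- (a) Define the event as first invasive ventilation or death, and label the Kaplan-Meier proportions *alive and never ventilated through Day X*.
- (b) At each landmark report the between-arm difference in Kaplan-Meier estimates with a 95% CI, for example with Greenwood variance or on the complementary log-log scale.
- (c) Present the log-rank test and Cox regression as whole-curve analyses of time to first ventilation or death, not as tests of the landmark proportions.
- (d) Name one main Day 60 analysis.
- (e) If status on the day is the intended outcome, report binary status with a risk difference and 95% CI instead, and state a rule for unknown status at each landmark.

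The cost of (a) to (d) is wording and a little more analysis, with no new data. Option (e) needs ventilation status at each landmark, which the listed outcomes already imply. The downside is that landmark intervals with 20 per arm will be wide; that width reflects the information available and should be shown.
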